The additional secondary efficacy endpoints will be analyzed applying the appropriate statistical method for the comparison of both treatment arms. For proportions, the Cochran-Mantel-Haenszel test (with stratification variable site) and the Pearson χ^2 -test will be applied. In case of a total number of observations below 30, or in case of at least one cell frequency below 5, Fisher's exact test will be used instead of the χ^2 -test. Two-sided 95% CIs for response rates will be calculated, where appropriate. Additionally the cumulative proportions of effects at weeks 1, 2, and 4 will be calculated.

All endpoints, with exception of “responder” 4 weeks after re-treatment, will be analyzed for the first treatment cycle only. The analysis of “responder” 4 weeks after re-treatment will be conducted on observed values only, i.e. subjects with missing investigator or the subject in-clinic assessments on FWS week 4 or at the preceding end of the cycle visit will be excluded from analysis. Subjects who were treated with placebo during the first treatment cycle are excluded from the analysis of this endpoint, but not assigned as being non-responders. A two-sided McNemar test (using a significance level of 0.05) will be used to compare the response proportions between week 4 re-treatment visit and at the preceding end of the cycle visit. This endpoint will be separately analyzed for each open label extension cycle.

Besides the FAS population for the analysis with multiplicity control, the analyses of these endpoints will also be based on the MFAS and the PP population. For all analyses, a one-sided significance level of 0.025 will be used, if not stated otherwise.

Additional exploratory subgroup analyses by geographic region, country, and site, or by subjects with previous use of botulinum toxin versus naïve subjects, will not be conducted for additional secondary analyses.

Secondary Safety Endpoints:

No statistical testing methods will be applied to statistically evaluate the differences on safety variables between treatment groups. Safety endpoint variables will be analyzed descriptively only.

Analysis of secondary safety endpoint 1 (adverse events):

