All laboratory values will be classified as normal or abnormal according to the central laboratory normal ranges and indicated as clinically significant (CS) or not clinically significant (NCS) by the investigator. Quantitative laboratory values will be summarized with means, standard deviations, medians, minima and maxima at baseline and over time and of absolute changes from baseline. Categorical variables will be summarized by counts and percentages of subjects in corresponding categories. Shift tables illustrating changes with respect to the central laboratory normal ranges and the investigator assessment between baseline and post-baseline visits will be created: Number and percentage of subjects with normal, CS and NCS laboratory values.

The analyses of variables for vital signs will focus on the evaluation of the change from baseline to the scheduled time points after baseline. Descriptive analysis with means, standard deviations, medians, minima and maxima of the time course and of changes from baseline to each post-baseline visit will be presented.

Normal/abnormal shift tables will be created for categorical variables of the overall ECG interpretation.

An additional safety evaluation will be performed by defining cycle 2 day 0 as baseline for subjects who switched from placebo to BoNT/A-DP.

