7 STATISTICAL CONSIDERATIONS AND ANALYSIS

7.1 Derived Variables

The below, table provide the list of derived variables for various duration derivations and baseline derivations applicable for this study.

Variables	Formula
Derivation of Duration	
Study day at any visit	Date of interest – date of first dose of study drug.
Extent of Exposure (Days)	Date of last study medication administration – Date of first study medication administration + 1
Extent of Exposure (Weeks)	Extent of exposure (days)/7
Baseline Derivations	
Baseline	The baseline value is defined as the last observation before treatment, i.e. pre-treatment values measured on the treatment day (baseline visit, day 0), and if missing or not evaluated, the value from screening visit.
Change from baseline	Post baseline value – Baseline value
Relative change from baseline	[(Post baseline value – Baseline value)/Baseline value]*100

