8.7.4 Laboratory data (secondary safety endpoint 3)

For the purposes of summarization in both the tables and listings, all laboratory values will be presented in SI units. If a lab value is reported using a nonnumeric qualifier e.g., less than (<) a certain value, or greater than (>) a certain value, the given numeric value will be used in the summary statistics, ignoring the nonnumeric qualifier.

Visit value and change and/or percent change from baseline (where applicable) during the treatment period will be summarized by treatment group using descriptive statistics for all laboratory parameters.

All laboratory values will be classified as normal or abnormal according to the central laboratory normal ranges and indicated as clinically significant (CS) or not clinically significant (NCS) by the investigator. Quantitative laboratory values will be summarized with means, standard deviations, medians, minima and maxima at baseline and over time and of absolute changes from baseline. Categorical variables will be summarized by counts and percentages of subjects in corresponding categories. Shift tables illustrating changes with respect to the central laboratory normal ranges and the investigator assessment between baseline and post-baseline visits will be created: Number and percentage of subjects with normal, CS and NCS laboratory values.

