8.7.6 Electrocardiograms (secondary safety endpoint 3)

Normal/abnormal shift tables will be created for the overall ECG interpretation by treatment group for all applicable time points.

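### Laboratory shift tables pool values below and above the reference range, so they lose direction and partly offset a one-directional effect

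*Protocol*

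**What the plan says.** SAP 8.7.4 starts from a two-state rule: "All laboratory values will be classified as normal or abnormal according to the central laboratory normal ranges". The investigator then rates values as clinically significant (CS) or not (NCS). Protocol 12.4.2 has the same rule. Both documents then describe the tables in the same words: "Shift tables illustrating changes with respect to the central laboratory normal ranges and the investigator assessment between baseline and post-baseline visits will be created", with the content given as "Number and percentage of subjects with normal, CS and NCS laboratory values".

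Two other laboratory summaries are planned. Protocol 12.4.2 states: "Quantitative laboratory values will be summarized with means, standard deviations, medians, minima and maxima at baseline and over time and of absolute changes from baseline". SAP 8.7.4 adds: "Visit value and change and/or percent change from baseline (where applicable) during the treatment period will be summarized by treatment group". SAP 7.1 defines change as "Post baseline value – Baseline value" and lists relative change separately, so the word absolute in the protocol means not relative; the sign is kept.

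No safety comparison is tested: "Safety endpoint variables will be analyzed descriptively only". Protocol 11.1.1 requires newly detected abnormal laboratory findings to be recorded as adverse events when the investigator judges them clinically significant.

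**The concern.** A reference range usually has two limits, and the three planned categories do not say which one was crossed. Protocol 11.15.1 lists haemoglobin, white cells, platelets, sodium, potassium and glucose, among others. A count of subjects who moved from normal to NCS on potassium would mix low and high results, and a reader could not interpret it clinically.

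There is also a loss of signal. If a treatment moves a parameter upward, more subjects go from normal to high and fewer from normal to low. A table that merges the two shows only the net change. What is at stake is how readable and how sensitive one descriptive safety table is, in a trial whose third secondary objective is a safety database to support approval.

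**Working it through.** The documents give no figure for the laboratory shift tables, so there is none to reproduce. The size of the offset has to be illustrated.

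**Input from the documents:** 525 subjects on BoNT/A-DP and 175 on placebo (protocol 12.1).

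**Assumptions, not in the documents:** normally distributed values; a two-sided range with 2.5% beyond each limit (±1.96 SD); a true upward shift d of 0.1 to 1.0 SD; a baseline to post-baseline correlation of 0.5 to 0.85. NCS and CS are added together as abnormal.

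**Step 1, one time point, d = 0.5 SD.**
- High: P(Z > 1.96 − 0.5) = 7.2%, against 2.5% with no effect, a rise of 4.7 points.
- Low: P(Z < −1.96 − 0.5) = 0.7%, against 2.5%, a fall of 1.8 points.
- Abnormal: 7.9%, against 5.0%, a rise of 2.9 points.
- Share offset: 1.8 / 4.7, about 38%.

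**Step 2, the shift table itself.** The bivariate normal distribution gives the cells of the low/normal/high table. The share offset is 1 − (excess normal-to-abnormal) / (excess normal-to-high), where excess means relative to d = 0. Shares come from unrounded cells.

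| Shift d (SD) | Excess normal-to-high, correlation 0.7 | Excess normal-to-abnormal, correlation 0.7 | Share offset, correlation 0.7 | Share offset, correlation 0.5 to 0.85 |
|---|---|---|---|---|
| 0.1 | 0.5 points | 0.1 points | 79% | 76-81% |
| 0.2 | 1.2 points | 0.4 points | 63% | 58-66% |
| 0.3 | 2.0 points | 1.0 points | 50% | 45-54% |
| 0.5 | 4.1 points | 2.7 points | 33% | 27-36% |
| 1.0 | 13.1 points | 11.5 points | 12% | 9-15% |

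In subjects, if all 525 are assessed at d = 0.5 and correlation 0.7, the excess is 525 × 0.0407, about 21, with high shown separately. It is 525 × 0.0275, about 14, in the merged table. For a parameter that can be abnormal on one side only, there is no opposite tail and the offset is zero.

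**Step 3, moves from one end of the range to the other.** Low-to-high plus high-to-low comes to at most about 0.1 expected subject in 525 per parameter and visit (d = 1.0, correlation 0.5).

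**Step 4, the planned mean change by arm.** In units of its standard error the difference is d / [√(2(1 − ρ)) × √(1/525 + 1/175)]. With ρ = 0.7 the denominator is 0.775 × 0.0873 = 0.0676. So d = 0.2 is about 3.0 standard errors and d = 0.5 about 7.4.

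**The case against.** The strongest reply is that the laboratory analysis as a whole does not hide such an effect. Step 4 shows that a uniform mean shift would stand out in the planned signed change by arm. Clinically significant abnormalities are also tabulated as adverse events by system organ class and preferred term (SAP 8.7.2), and every value is listed by subject (SAP 8.1). This stands, and it limits the point. It does not remove it. Mean change does not count subjects who cross a limit, adverse event tables leave out NCS abnormalities, and listings are not summaries by arm.

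A second reply is that SAP section 1 places the table templates in a separate document, which may split low and high. That is possible. But the SAP names the categories, and a programmer who follows it would not split them.

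Four stronger readings are tempting, and the documents do not support them:
- That a one-directional effect is largely cancelled. This is so only for small shifts on two-sided ranges; at 0.5 SD most of the excess remains.
- That a low-to-high move appears as no shift. This needs the same CS/NCS rating at both visits, since low NCS to high CS does register. Step 3 shows such moves are very rare in any case.
- That the shift tables are the only categorical comparison of laboratory safety. The adverse event tables are another.
- That the ECG tables, described as "Normal/abnormal shift tables will be created for the overall ECG interpretation by treatment group", hide a worsening from NCS to CS. Neither document says that such a rating is recorded for the ECG.

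**Conclusion.** The point holds in a limited form. As written, the shift tables cannot show whether an abnormal laboratory value is low or high, and that follows from the text alone. The partial offset of a one-directional effect depends on the assumed range, distribution, shift and correlation: about 60-80% of the excess at 0.1-0.2 SD, about half at 0.3 SD, about a third at 0.5 SD and about a tenth at 1.0 SD. The documents give no reference ranges, so which parameters have two limits is also an assumption. The loss is confined to one descriptive table, and no test or efficacy conclusion depends on it. This is a worthwhile improvement to the safety reporting, not a flaw that threatens the trial.

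**What to change.** In protocol 12.4.2 and SAP 8.7.4, define the laboratory shift tables as low / normal / high against the central laboratory range, baseline by each post-baseline visit and by treatment group. Show the investigator's CS or NCS judgement within low and within high. If the protocol text is left as it is, list the change in SAP section 9. Both documents already rely on the central laboratory ranges and the investigator's ratings, so no new data are needed. The cost is SAP wording, matching table templates and slightly longer tables.

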12.4.3 Further Analyses

Baseline data, including demographic data will be analyzed descriptively. Subject disposition, including discontinuation and reasons for discontinuation, and subject exposure will be tabulated in detail. Concomitant medication, including application site concomitant medication, will be coded according to the World Health Organization (WHO) drug dictionary and tabulated accordingly.

12.5 General Statistical Considerations

The statistical analysis of the first treatment cycle and the open label extension phase (cycles 2-4) will be performed after database lock of all data up to the end of study (can take place in four-weekly intervals from study week 48 until study week 60 [see schedule of study procedures and assessments Section 2.1]) and final unblinding.

Further aspects of statistical analyses will be detailed within a SAP. This plan will be finalized prior to the database lock and/or study unblinding.

Continuous variables will be summarized with means, standard deviations, medians, minima and maxima. Categorical variables will be summarized by counts and by percentages of subjects in corresponding categories.

For statistical analyses “baseline” refers to the last observation before treatment, i.e. pre-treatment values measured on the treatment day (baseline visit, day 0), and if missing or not evaluated, values from screening visit will be used.

Analyses will be performed by visit, irrespective of any time window deviations.

12.5.1 Demographic and Baseline Characteristics

Summary statistics will be provided by treatment group for demographics (e.g. age, gender, race, ethnicity, Fitzpatrick skin type) and for baseline characteristics.

For all efficacy endpoints, baseline will be defined as the measurement prior to receipt of the first dose of study medication.

12.5.2 Interim Analysis

There will be no formal interim analysis during the study.

13. DIRECT ACCESS TO SOURCE DATA/DOCUMENTS

The investigator/study site will cooperate and provide direct access to study-related records and data, including source documentation for monitoring by the study monitor or authorized representatives of the Sponsor, audits by the Sponsor or authorized representatives of the Sponsor, EC review, and applicable regulatory authority inspections. If contacted by applicable regulatory authorities, or during an inspection, the investigator will notify the Sponsor of contact, cooperate with the authorities, provide the Sponsor with copies of all documents received from the authorities, and allow the Sponsor to comment on any responses. In the event of an inspection, the investigator agrees to allow the inspector direct access to all relevant documents and to allocate his/her time and that of the study site personnel to the inspector to discuss findings in any relevant issues. The investigator will allow CROMA Pharma GmbH personnel to be present as an observer during a regulatory inspection, if requested.

14. QUALITY CONTROL AND QUALITY ASSURANCE

Standard Operating Procedures (SOPs) belonging to [REDACTED] will be adhered to for all activities relevant to the quality of the study, and performed by [REDACTED] employees, and are routinely monitored by the [REDACTED] [REDACTED] [REDACTED] [REDACTED]. Vendors sub-contracted by [REDACTED] or CROMA Pharma GmbH will adhere to their own relevant SOPs.

A Sponsor-designated, monitor (independent to the site) will be responsible for the monitoring of the study and its data within the CRFs. The monitoring of the study will be performed according to [REDACTED] monitoring SOPs.

14.1 Investigator's Responsibility

The investigator will comply with the protocol, ICH GCP, and applicable regulatory requirements and local laws and regulations. The investigator is ultimately responsible for the conduct of all aspects of the study at the study site. The investigator verifies by signature the integrity of all data transmitted to the Sponsor. Except where the investigator's signature is specifically required, it is understood that the term "investigator", as used in this protocol, and in study-related documents refers to the investigator or authorized study personnel that the investigator has designated to perform a certain duty. Sub-investigators or other authorized study personnel are eligible to sign for the investigator, except where the investigator's signature is specifically required.

14.2 Study Organization

The name and contact information of all of the individuals involved with the study (e.g. investigator(s), medical director, authorized representative(s) of the Sponsor, laboratories, steering committees, and oversight committees, if applicable) will be maintained by the Sponsor and provided to the investigator.

14.3 Training

The study monitor or authorized representatives of the Sponsor will ensure that the investigator and study site personnel understand all requirements of the protocol, the study status of the IMP, and his/her regulatory responsibilities as an investigator. Training may be provided at an investigator's meeting, at the study site, and/or by instruction manuals. In addition, the study monitor or authorized representatives of the Sponsor will be available for consultation with the investigator, and will serve as the liaison between the study site and the Sponsor.

14.4 Monitoring

The study monitor and/or other authorized representatives of the Sponsor is/are responsible for monitoring that each study site conducts the study according to the protocol, SOPs, other written instructions, ICH GCP, and applicable regulatory guidelines. The investigator will permit the study monitor or other authorized representatives to visit the study site at appropriate intervals to observe the progress of the study, review study records/documentation, and ensure that informed consent has been obtained for each subject prior to performing any study procedure. Monitoring processes specific to the study will be described in the clinical monitoring plan.

14.5 Auditing

The Sponsor and/or Sponsor's representatives may conduct audits (quality assurance) to evaluate study conduct and compliance with the protocol, SOPs, other written instructions/agreements, ICH GCP and applicable regulatory guidelines/requirements.

The investigator will permit auditors to visit the study site. The quality assurance auditor will have access to all medical records, the investigator's trial-related files and correspondence, and information in the informed consent documentation of this clinical trial.

14.6 Non-compliance with the Protocol

The investigator may deviate from the protocol to eliminate an apparent immediate hazard to the subject or when the change(s) involves only logistical or administrative aspects of the study (e.g. change of phone number). In the event(s) of an apparent immediate hazard to the subject, the investigator will notify the Sponsor immediately by phone and confirm notification to the Sponsor in writing as soon as possible, but within 1 calendar day after the change is implemented. The Sponsor, or authorized designee, will also ensure the responsible EC is notified of the urgent measures taken in such cases according to local regulations.

If monitoring and/or auditing identify serious and/or persistent non-compliance with the protocol, the Sponsor may terminate the investigator's participation. The Sponsor will notify the EC and applicable regulatory authorities of any investigator termination.

15. ETHICS

15.1 Basic Principles

This research will be carried out in accordance with the current versions of the Declaration of Helsinki; the ICH harmonized tripartite guideline regarding GCP (E6 Consolidated Guidance, April 1996), and local regulatory requirements.

15.2 Ethics Committee and Regulatory Authorities

Before enrollment of subjects into this study, the protocol, ICF and any promotional material or advertisements will be reviewed and approved by the appropriate EC and regulatory authorities, where applicable. The IB will be provided for review. The study will commence only when the committee has approved the protocol or a modification thereof and a copy of the approval letter is received by CROMA Pharma GmbH.

If a protocol is substantially amended, the protocol amendment, revised ICF (if applicable), and any revised promotional material or advertisements will be reviewed and approved by the appropriate EC and regulatory authorities, where applicable. A substantial protocol amendment will only be implemented upon the Sponsor's receipt of approval and, if required, upon the Sponsor's notification of Regulatory Authority(ies) approval.

It is the investigator's responsibility to obtain EC approval for the protocol and all subsequent major changes, in compliance with local law.

15.3 Informed Consent

Investigators will choose subjects in accordance with the eligibility criteria.

It is the investigator's or designee's (where applicable) responsibility to explain the trial to each potential subject and obtain written informed consent (stating clearly that the study includes the possibility of up to three repeat treatments depending on a number of factors) before any trial procedures are performed.

The purpose of the study, procedures to be carried out, and potential risks will be described to the subjects in non-technical terms in the SIS. Subjects will be required to read, sign, and date the ICF, summarizing the discussion prior to screening, and will be assured that they may withdraw from the study at any time without jeopardizing their medical care.

Subjects will sign and date one copy of the ICF, the investigator/designee providing the information and obtaining the consent will also sign. The copy will be retained by the subject and the original will be retained on file by the investigator. The copy of the SIS will also be given to the subject.

By signing the ICF, subjects agree that they will complete all evaluations required by the study, unless they withdraw voluntarily or are terminated from the study for any reason.

The Sponsor will provide to the investigator in written form any new information that significantly impacts the subjects' risks associated with IMP exposure. The SIS and ICF will be updated, if necessary.

16. DATA HANDLING AND RECORD KEEPING

All raw data generated in connection with this study (and site files), together with the original copy of the final report, will be retained in the archives of [REDACTED] until at least five years after the last approval of a marketing application in an ICH region and until there are no pending or contemplated marketing applications in an ICH region or at least five years have elapsed since the formal discontinuation of clinical development of BoNT/A-DP. These documents will be retained for a longer period if required by the applicable regulatory requirements, or by an agreement with the Sponsor. The trial master file (TMF) will be archived by the Sponsor.

The study site should maintain a study file, which should contain, at minimum, the IB, the protocol and any amendments, drug accountability records, correspondence with the Independent Ethics Committee (IEC)/Institutional Review Board (IRB) and the Sponsor (or designee), and other study-related documents.

The investigator agrees to keep records and those documents that include (but are not limited to) the identification of all participating subjects, medical records, study-specific source documents, source worksheets, all original signed and dated ICFs, copies of all CRFs, query responses, and detailed records of drug disposition to enable evaluations or audits from regulatory authorities.

The investigator should retain records required to be maintained for a period of five years following the date a marketing application in an ICH region is approved for the drug for the indication for which it is being investigated or, if no application is to be filed or if the application is not approved for such indication, until at least five years after the investigation is discontinued. However, these documents should be retained for a longer period if required by the applicable regulatory requirement(s) or if needed by the Sponsor. In addition, the investigator must make provision for the subjects' medical records to be kept for the same period of time.

No data should be destroyed without the agreement of CROMA Pharma GmbH. Should the investigator wish to assign the study records to another party or move them to another location, CROMA Pharma GmbH must be notified in writing of the new responsible person and/or the new location.

Subjects' medical records and other original data will be archived in accordance with the archiving regulations or facilities of the investigational site.

